Figure 1,2. The patients were randomly divided into two groups, who will accept the treatment of involved-field radiotherapy (RT) combined with concurrent intrathecal-MTX or intrathecal-ara-C, respectively. Concomitant regimen consisted of intrathecal chemotherapy (via lumbar puncture, MTX 15 mg, plus dexamethasone 5 mg, or ara-C 50mg, plus dexamethasone 5 mg, once per week, 4 weeks in total) and RT. RT consisted of fractionated, conformal radiation given at a daily dose of 2 Gy. The planning volume consisted of sites of symptomatic disease, bulky disease observed on MRI, including the whole brain and basis cranii received 40 Gy in 20 fractions and/or segment of spinal canal received 40-50 Gy(the first lumbar vertebra and the above segments were given 40 Gy in 20 fractions; the first lumbar vertebra and the inferior segments were given 40/50 Gy in 20 fractions). Patients with Karnofsky performance status score (KPS) of ≤ 40 and irradiation intolerance were required to receive induction intrathecal chemotherapy (MTX 15 mg, or ara-C 50mg, plus dexamethasone 5 mg, twice per week). Then these patients were allowed to receive concomitant therapy upon neurologic improvement and radiotherapy tolerance.

The primary endpoint was clinical response rate (CRR). The secondary endpoints were safety and overall survival (OS).

Methods:

We adopted the criteria of evaluation for clinical response established in our previous study based on improvement of neurologic symptoms/signs and changes of KPS ^[1]. The criteria have been proved associated with the prognosis of LM patients and suitable for clinical application. The clinical response was evaluated by at least two experienced neuro-oncologists. The evaluation consists of 5 layers, including complete response (CR), obvious response (OR), partial response (PR), stable disease (SD) and progressive disease (PD) (Table 1). Clinical evaluation was performed once per week from the beginning of LM-related therapy, till 2 weeks later after salvage therapy.

Clinical response was defined as continuous presence of CR, OR or PR within an interval of at least 1 week. SD and PD were defined as ineffective. Adverse events (AEs) were evaluated according to the Common Terminology Criteria for Adverse Events (CTCAE, version 3.0). Events of grade 3~5 was defined as moderate and severe adverse events. Survival time was measured from the enrollment of the study until death or the last follow-up.

[figure not shown]

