Statistical Analysis Plan

SPSS 17.0 software was used for data analysis. Survival analysis was performed using the Kaplan-Meier method. Log-Rank test was used to compare the survival time of patients. Univariate and multivariate Cox regression analysis were carried out to determine the risk factors of OS. Chi square test and Fisher exact test were used to evaluate the difference of clinical response rate and OS between patients with various features. $P < 0.05$ demonstrated significant difference.

References:

[figure not shown]
Figure 1

LM: Leptomeningeal metastasis;
IC: intrathecal chemotherapy;
Ara-C: Cytarabine ;
OS: overall survival;

RT: involved-field radiotherapy;
MTX: Methotrexate ;
CRR: clinical response rate;
AD: adverse events.

Figure 2

IF-RT: involved-field radiotherapy; IC: intrathecal chemotherapy.

↓ Involved-field radiotherapy: daily: 20 × 200 cGy, total dose: 40 Gy.

↑ Intrathecal chemotherapy: Methotrexate 10 mg/ Cytarabine 50mg+dexamethasone 5 mg.

* Induction therapy were those with a Karnofsky performance status score of ≤ 40 and with no tolerance to radiotherapy.

Table 1 **Criteria of clinical response evaluation**

	Neurological symptoms and signs	KPS score
Complete response	Almost normal neurological examination. Mild cranial nerve symptoms including tinnitus or blurred vision may exist. GCS score of 15.	≥90
Obvious response	Significant neurologic improvement. No severe symptoms/signs, such as severe headache, somnolence, mental status. Dizziness, confusion, mild headache, cranial nerve paralysis, or radiculitis may exist. GCS≥12.	≥ 70, or elevation of ≥ 30 compared with the baseline level.
Partial response	Partial neurological improvement. Still with headache, or other mild/moderate symptoms/signs. GCS≥9.	50-70, or elevation of 10-20 compared with the baseline level.
Stable disease	No visible neurological improvement.	Elevation of ≤ 10 compared with the baseline level.
Progressive disease	Deteriorative neurological symptoms and signs.	Decrease of KPS compared to the baseline level.

Two conditions both of neurological symptoms/signs and KPS must be satisfied synchronously.

KPS, Karnofsky performance status score; GCS, Glasgow Coma Scale.

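### Table 1 caps the KPS condition for partial response from above, so a partly improved patient who goes from KPS 50 to 80 fits no row while one who goes from 50 to 70 is a responder

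*Combined protocol and SAP*

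**What the plan says.** The Design section makes CRR the primary endpoint. The Methods section then defines it: "Clinical response was defined as continuous presence of CR, OR or PR within an interval of at least 1 week". The two remaining classes are non-response: "SD and PD were defined as ineffective".

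Table 1 has one column for neurological findings and one for KPS. The PR row reads "Partial neurological improvement. Still with headache, or other mild/moderate symptoms/signs. GCS≥9" in the first and "50-70, or elevation of 10-20 compared with the baseline level" in the second. The OR row has no upper limit on KPS ("≥ 70, or elevation of ≥ 30 compared with the baseline level"), but its neurological column asks for significant improvement, no severe symptoms or signs, and a GCS of at least 12. The SD row needs no visible neurological improvement together with "Elevation of ≤ 10 compared with the baseline level". The PD row needs neurological deterioration and a fall in KPS.

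The footnote ties the columns together: "Two conditions both of neurological symptoms/signs and KPS must be satisfied synchronously". Nothing in the documents says how to class a patient whose two columns point to different rows, or that the table is read from the top.

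**The concern.** A response scale should not turn a responder into a non-responder because the patient did better on one component while the other stayed the same. Table 1 can do that. The PR row stops at KPS 70 or at a gain of 20, and the next row up cannot be reached without a better neurological grade. A patient with partial neurological improvement and a high KPS is therefore left between PR and OR.

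The primary endpoint is at stake. A rater who meets such a patient has two choices: apply the table literally and lose a patient who improved, or raise the neurological grade from partial to significant so that OR fits. The documents describe neither blinding of the assessors nor a rule for discordant columns, so the second choice puts discretion into the endpoint that is compared between the arms.

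**Working it through.** **Inputs.** All conditions come from Table 1 and its footnote. Two assumptions are mine: KPS moves in steps of 10 from 10 to 100, and the neurological grade is held at partial improvement throughout. Write b for baseline KPS and f for current KPS.

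- PR, KPS column: 50 ≤ f ≤ 70, or 10 ≤ f − b ≤ 20.
- OR, KPS column: f ≥ 70, or f − b ≥ 30. The neurological column fails, because improvement is only partial.
- CR, SD and PD: the neurological column fails in each, because the examination is not almost normal, there is visible improvement, and there is no deterioration.

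With partial improvement, PR is thus the only row open, and everything depends on its KPS condition. The plan states no figure of its own to reproduce here.

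**Step 1: two patients side by side, both b = 50.**

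- f = 70: 50 ≤ 70 ≤ 70 holds, and the gain of 20 also qualifies. PR.
- f = 80: 80 is above 70, and the gain of 30 is above 20. Both alternatives fail. No row.

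The same reversal occurs from b = 10. A rise to 30 (gain 20) is PR, a rise to 40 (gain 30, but f below 50) is not, and a rise to 50 is PR again.

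**Step 2: all pairs with a gain of at least 30.**

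| Current KPS | Baselines with gain ≥ 30 | Pairs | PR KPS condition |
|---|---|---|---|
| 40 | 10 | 1 | fails |
| 50 | 10, 20 | 2 | met |
| 60 | 10 to 30 | 3 | met |
| 70 | 10 to 40 | 4 | met |
| 80 | 10 to 50 | 5 | fails |
| 90 | 10 to 60 | 6 | fails |
| 100 | 10 to 70 | 7 | fails |

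Total 1 + 2 + 3 + 4 + 5 + 6 + 7 = 28. Met: 2 + 3 + 4 = 9. Failed: 1 + 5 + 6 + 7 = 19, of which 18 end at KPS 80 or more. All 19 satisfy the OR condition on KPS and miss OR on the neurological column alone.

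**Step 3: no gain.** For f = b, the gain alternative fails and only the 50-70 band is left. Stable at 60 or 70 is PR; stable at 80 or 90 is not. So a large gain is not needed to fall into the gap.

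**Step 4: repeated visits.** Response has to be held for at least a week. A patient who held PR for that long at KPS 60-70 and then rose to 80 has already qualified. One who passes through the band in less than a week, or jumps over it, has the run broken by an unclassified visit.

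**Step 5: after the change.** With the PR condition as f ≥ 50 or f − b ≥ 10, and f ≥ b required when f ≥ 80, all 28 pairs meet it: 27 have f ≥ 50 and none of these is a fall, and 10 to 40 has a gain of 30. Stable 80 and 90 also meet it. A fall from 90 to 80 still does not.

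**The case against.** Four objections have force.

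First, the two alternatives in the PR cell are joined by an or. A reader might infer that any gain above 20 disqualifies the patient. It does not: 30 to 70 or 40 to 70 remains PR because the final score lies in the band. This stands, and it limits the point to patients who end outside 50-70.

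Second, partial and significant improvement have no written threshold. A patient with moderate headache and a GCS of 14 is not plainly excluded from OR, whose row rules out severe headache and tolerates mild headache but does not mention moderate. A rater could record OR without breaking a rule. This stands too: the loss is certain only once the neurological grade is settled as partial. But a rater's freedom to move the grade does not remedy the KPS ceiling.

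Third, the scale of the problem is unknown. Of the 19 failing pairs, 13 (6 + 7) end at KPS 90 or 100, the level required for CR, and that may be rare with only partial improvement. A reader might take 19 of 28 as a share of patients lost. It is a count of grid cells with equal weight, and the documents give no KPS distribution from which to derive a share.

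Fourth, the same table and at least two assessors apply in both arms, and the criteria come from an earlier study. A reader might infer bias between the arms; the documents do not show it. Prior use of the criteria does not tell an assessor how to class these patients, and no text in these documents fills the gap.

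**Conclusion.** The point holds in limited form. For a patient with only partial neurological improvement, Table 1 as written has no row for a KPS of 80 or more reached without a gain of 10-20, nor for 10 to 40. Such a visit is unclassified; it is not SD or PD. It fails to count as response only because response requires CR, OR or PR. The primary endpoint is therefore not monotone in functional outcome.

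The size is 19 of 28 score pairs with a gain of at least 30, plus stable 80 and 90. This rests on 10-point KPS steps, a literal reading of the footnote, and a neurological grade fixed at partial. The number of patients affected and the change in CRR cannot be computed.

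A reader might also infer that the other empty cells distort CRR, for example no visible improvement with a KPS gain of 20, or deteriorating signs with unchanged KPS. They do not: these patients are not responders on any reading. They only prevent the five classes from adding up to all patients.

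A change is still warranted, because a stated rule of the primary endpoint can drop a patient for doing better and the repair is small.

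**What to change.** In the PR row of Table 1, replace the ceilings with lower bounds: KPS of at least 50, or a gain of at least 10. For the newly admitted values of 80 or more, require that KPS has not fallen from baseline. Without that clause a fall from 90 to 80 with partial improvement would become a response, which it is not under the present table. Add to the footnote that a patient takes the best row for which both columns are met.

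Separately, and with no effect on CRR, state that any rated patient not in CR, OR or PR counts as ineffective, so that the classes add up to everyone rated.

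The cost is one edit to the table and its footnote. No new data are needed, provided that the neurological grade and KPS are recorded separately at each visit. The change can only add PR ratings, so CRR can rise or stay the same but cannot fall. The downside is slightly less comparability with the earlier single-arm study; reporting CRR under the present table alongside the revised one covers that and shows how many patients the ceilings affected.
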